IRB-HSR# 17224: Randomized, Placebo-controlled, Single Blind, Trial to Determine the Safety and Efficacy of Ticagrelor for Maintaining Patency of Arterio-Venous Fistulae Created for Hemodialysis

flow will be obtained using ultrasound dilution by transonics which is a standard of care procedure. Any change in the clinical assessment of the access, prolonged bleeding (>20 minutes) after removal of needles, trend of decreasing intra-access blood flow as determined by transonic (> 25% or original flow), or an access flow rate < 400 ml/min, will prompt a referral for a fistulogram. If confirmed stenosis (>50% stenosis of the access diameter) an intervention (angioplasty) will be performed. This intervention is part of the study patient's standard of care. Timeline of study: -6 Months recruitment phase -6 months active study phase: -6 months follow up: both groups will be monitored by complete physical examination, laboratory and dialysis data as well as monthly transonic assessment of intra-access blood flow rate will be done for standard of care and we will document if any intervention is required. -6 months statistical analysis and data documentation

Objectives: The primary objective is to evaluate the feasibility and safety of Ticagrelor in hemodialysis patients with AVF vascular access.

The secondary objective is to evaluate the treatment efficacy of Ticagrelor to see if it will preserve patency of hemodialysis vascular access better than Placebo.

Study Design: Biomedical

1. Will controls be used?

Yes

► IF YES, explain the kind of controls to be used.

Yes, we will have a group of study subjects that will be given a placebo in addition to what they would get that is the current standard of care for their medical issue.

2. What is the study design?

This is a randomized, placebo-controlled, single-blind study.

3. Does the study involve a placebo?

Yes

► IF YES, provide a justification for the use of a placebo

The placebo group can be used as an "add on" to standard of care in comparison to an investigational treatment added to standard of care. This is what will happen in this study.

Human Participants

Ages: 18 to 85

Sex: Male and Female

Race: All

Subjects- see below

1. Provide target # of subjects (at all sites) needed to complete protocol.

70

2. Describe expected rate of screen failure/ dropouts/withdrawals from all sites.

25%

3. How many subjects will be enrolled at all sites?

88

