IRB-HSR# 17224: Randomized, Placebo-controlled, Single Blind, Trial to Determine the Safety and Efficacy of Ticagrelor for Maintaining Patency of Arterio-Venous Fistulae Created for Hemodialysis

4. How many subjects will sign a consent form under this UVa protocol?

88

5. Provide an estimated time line for the study.

We hope to have enrollment completed within 6 months of protocol approval.

Inclusion/Exclusion Criteria

1. List the criteria for inclusion

- Patients on chronic hemodialysis with a functioning arterio-venous fistula
- Subjects must agree to use adequate contraception to prevent pregnancy

2. List the criteria for exclusion

- Hemoglobin less than 9g/dL per chart review of the last Hemoglobin level obtained for standard of care.
- If the study subject can't be washed off of anti-coagulants or antiplatelets
- Recent history of bleeding over the last 3 months preceding enrollment
- History of bleeding disorder (hemophilia, Von Willebrandt disease, etc....). Anemia only if it is chronic and thrombocytopenia if the platelet count is consistently <125,000.
- Recent history of blood transfusion over the last 3 months preceding enrollment
- Recent serious injury or surgery over the last 3 months preceding enrollment
- History of gastro-intestinal ulcers
- Moderate-severe hepatic impairment (ALT/AST greater than 3-5 times the upper limit of normal).
- Uncontrolled blood pressure (SBP> 190 or DBP >110) pre or post dialysis
- History of stroke within the last 5 years.
- Pregnant females-self reported
- Hypersensitivity to Aspirin /antiplatelets
- Subjects using peroral anticoagulants
- History of intracranial hemorrhage
- Active pathological bleeding
- Hypersensitivity to ticagrelor or any component of the product

3. List any restrictions on use of other drugs or treatments.

Subjects using peroral anticoagulants will be excluded to avoid excessive bleeding risk. There will be a 4 day wash off for subjects who are taking anticoagulants and anti-platelets. If subjects can't be washed off of these medications then they cannot be included in the study.

Statistical Considerations

1. Is stratification/randomization involved?

Yes

► **IF YES, describe the stratification/ randomization scheme.**

Every other study subject will be on active study drug. Investigators and study personnel will be un-blinded.

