Due to the pilot nature of this study, formal power analysis and sample size estimation is not essential. Nevertheless, we attempted to estimate the potential treatment efficacy in this study. We considered the outcome measure for efficacy evaluation is the time to first stenosis event during the study period. From our recent clinical data, it was estimated that approximately 36% of dialysis patients experienced stenosis event at one-year follow-up. We would expect that patients in the new drug arm would have 10% stenosis event rate at one-year follow-up, compared to the 36% stenosis event rate in the placebo group. With these considerations, the analysis of stenosis-free survival will require at least 21 events, which is the number of events needed for one-sided log-rank test at 5% significance level to have 80% power to show statistically significant difference when the true hazard ratio is 0.236. This estimation will result in that approximately seventy patients will be needed and evenly randomized into each study arm (35 patients in Ticagrelor and 35 in placebo). This is an open-label study. Upon completion of all the required screening assessments, eligible patients will be randomly assigned to the study drug or placebo at 1:1 ratio with a block size of 20 in accordance with the randomization schedule. The randomization schedule will be provided by the Department of Public Health, School of Medicine. Patients will be identified by unique subject identifier that will remain consistent for the duration of the study. The active study period is 6 months followed by 6 months of monitoring, and accrual rate is approximately 12 patients per month. To compensate for an estimated drop-out rate of 25%, we will recruit 88 patients to the study.

4. What is your plan for primary variable analysis?

We have recruited/consented a total of 54 subjects into this study. We have enrolled a total of 43 patients into the study, 23 in the Ticagrelor treatment arm and 20 in the placebo arm. We will evaluate the safety of Ticagrelor in hemodialysis patients with AVF vascular access by tabulating adverse events and severe adverse events for the two study arms, and the difference between the two arms will be tested by chi-square test.

5. What is your plan for secondary variable analysis?

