- Weekly Hemoglobin Tests

2.3 Under what criteria would an INDIVIDUAL SUBJECT’S study treatment or study participation be stopped or modified

At subject, PI or sponsor’s request

Treatment would be stopped if the subject had a serious adverse event deemed related to study

Subjects will be stopped if they meet one or more of the study stopping rules

2.4 Under what criteria would THE ENTIRE STUDY need to be stopped.

IRB-HSR# 17224: Randomized, Placebo-controlled, Single Blind, Trial to Determine the Safety and Efficacy of Ticagrelor for Maintaining Patency of Arterio-Venous Fistulae Created for Hemodialysis

*These are called stopping rules for early termination of the entire study.
List criteria regardless of whether the study is sponsored or not.
Be sure to include any criteria for which the UVa PI would halt the study at UVa.*

Per IRB, PI, DSMB, or sponsor discretion

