5.1. Who is responsible for overseeing safety data for this study ?

- No additional oversight body other than PI at UVa Skip question 5.2

5.2. What is the composition of the reviewing body and how is it affiliated with the sponsor? N/A

5.3. What items will be included in the aggregate review conducted by the PI?

- All adverse events
- Unanticipated Problems
- Protocol violations
- Audit results
- Application of dose finding escalation/de-escalation rules

These should be outlined under 2.4.
- Application of study designed stopping/decision rules
- Early withdrawals
- Whether the study accrual pattern warrants continuation/action
- Endpoint data

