5.4 How often will aggregate review occur?

For additional information on aggregate review see:
www.virginia.edu/vpr/irb/hsr/continuations.html#aggreview

- Annually

5.5. How often will a report, regarding the outcome of the review by the DSMB/DSMC, be sent to the UVa PI?

IRB-HSR# 17224: Randomized, Placebo-controlled, Single Blind, Trial to Determine the Safety and Efficacy of Ticagrelor for Maintaining Patency of Arterio-Venous Fistulae Created for Hemodialysis

A copy of these reports must be sent to the IRB if applicable as soon as they are received by the PI. Do not wait until the next continuation to submit them to the IRB.

NA- PI is the overall person overseeing the safety data for this study.

5.6. How will a report of the information discussed in question 5.4 OR 5.5 be submitted to the IRB?

Part of IRB-HSR continuation status form

Payment

What is the difference between compensation and reimbursement?

A reimbursement is used when the subject is paid back for travel expenses such as mileage, lodging, food while traveling. Receipts or mileage must be submitted for a reimbursement.

Compensation is "payment" for things such as time, discomfort, inconvenience.

Total possible compensation should reflect the true value of the total possible dollar amount per participant for one year involvement in the study whether it be cash, check, gift card, goods, etc. or a combination of these items.

Retention "Gifts"- gifts may be given to a subject periodically during the study to remind them they are in the study. Sponsors may provide such items as water bottles, birthday cards etc. to the subject. NOTE: Cash or gift cards are NOT allowed as retention items.

1. Are subjects being reimbursed for travel expenses (receipts /mileage required)?No

2. Are subjects compensated for being in this study?

Yes

2a. What is the maximum TOTAL compensation to be given over the duration of the protocol?

\$415.00

2b. Explain compensation to be given.

- For the screening visit subjects will be compensated \$25.00 due to length of time necessary to complete this visit.
- For the first 6 months of study participation, when subjects are on ticagrelor or placebo (visit 1 to visit 12) subjects will be compensated \$25.00 for their time in completing these visits.
- For the last 6 months of study participation, when study subjects will **not** be taking ticagrelor or placebo subjects will be compensated \$15.00 for their time in completing these visits.

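### Aggregate safety review is annual, so on the planned timeline 98% to 100% of dosing precedes it; the stopping clause also names a DSMB that the plan does not have

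*Combined protocol and SAP*

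**What the plan says.** All section numbers refer to the Data and Safety Monitoring Plan unless stated otherwise.

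- **2.4** asks for the criteria for stopping the entire study. The whole answer is "Per IRB, PI, DSMB, or sponsor discretion".
- **5.1** names the PI alone: "No additional oversight body other than PI at UVa". Section 5.2, on the composition of a reviewing body, is marked not applicable. Section 5.5, on DSMB reports, is answered "NA- PI is the overall person overseeing the safety data for this study".
- **5.3** lists what the PI's aggregate review covers, including "Application of study designed stopping/decision rules". It points to 2.4 for the rules. It does not say that the review is done by arm.
- **5.4** puts the question "How often will aggregate review occur" and answers that it is once a year. Under 5.6 the report goes to the IRB with the continuation form.
- **Timeline.** The section Hypothesis to be Tested gives "6 Months recruitment phase -6 months active study phase: -6 months follow up". Human Participants adds "We hope to have enrollment completed within 6 months of protocol approval". Statistical Considerations, item 3, says that the "accrual rate is approximately 12 patients per month" and that 88 will be recruited to obtain 70. The opening study summary and the pharmacy appendix both give six months of dosing per subject.

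**The concern.** Safety and feasibility are the primary objective. The protocol describes the drug as untested in ESRD and lists severe bleeding among its risks. An excess of bleeding in one arm shows up when events are counted across subjects by arm, and the aggregate review is the only scheduled step that looks across subjects during the trial. If it falls after nearly all dosing, it can inform the final report but can do little for the subjects exposed.

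The stopping provision has two further faults. It names a body that the plan says does not exist. It also holds no rule, although 5.3 expects the review to apply one.

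**Working it through.** **Inputs.** Dosing is 6 months per subject. Accrual is 12 per month. The plan needs 70 to complete and will recruit 88. Review is every 12 months.

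**Assumptions.** Entry is uniform, every subject takes the full six months, and the 12-month clock starts at first enrolment. The documents do not say when the clock starts.

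**Step 1: the plan's own enrolment period.** 70 / 12 = 5.83 months, and 12 × 6 = 72, so six months is reproduced for 70 subjects. For 88, 88 / 12 = 7.33 months, which does not fit six. Both are carried forward.

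**Step 2: share of dosing delivered by month 12.** A subject entering at time e has received min(6, max(0, T − e)) months of dosing by time T. The share is the mean of this over all subjects, divided by 6.

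- 70 subjects: the last entrant has had 12 − 5.83 = 6.17 months on study, so all are finished and the share is 100%.
- 88 subjects: 12 × 6 = 72 entered by month 6 and are finished (72 / 88 = 81.8%). The other 16 (18.2%) have received between 6 and 4.67 months, on average 5.33, or 88.9% of their dosing. The share is 0.818 + 0.182 × 0.889 = 0.980. The last dose falls at 7.33 + 6 = 13.3 months.

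If subjects enter one at a time, every 1/12 month from time zero, 73 of 88 (83%) are finished and the share is still 98%.

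**Step 3: where earlier reviews would fall.** At month 3 the share is (3 / A) × (1.5 / 6), where A is the enrolment period. The later months use the formula in step 2.

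| Review at month | 70 subjects (A = 5.83) | 88 subjects (A = 7.33) |
|---|---|---|
| 3 | 12.9% | 10.2% |
| 6 | 51.4% | 40.9% |
| 9 | 88.5% | 78.7% |
| 12 | 100% | 98.0% |

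**Step 4: other clocks and slower enrolment.**

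- Clock starts at approval, and 88 subjects begin entering 1, 2 or 3 months later: the month-12 share is 93.8%, 87.4% or 78.7%.
- Clock starts at first enrolment, with enrolment over 12 months: half are finished and the other half have had on average half their dosing, so 0.5 + 0.5 × 0.5 = 75%.
- Over 18 months: one third are finished, one third have had on average half, and one third have not entered, so 0.333 + 0.167 = 50%.
- Over 24 months: 0.25 + 0.25 × 0.5 = 37.5%.

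The 12, 18 and 24 months are assumptions. Statistical Considerations, item 4, reports 43 enrolled but gives no dates, so actual accrual cannot be worked out.

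**Step 5: what operates between annual reviews.**

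| Safeguard | Place | Compares the arms? |
|---|---|---|
| Visits twice a month on drug | 2.2 | No, single subjects |
| Bleeding and hemoglobin hold rules | Biomedical Research, item 1 | No, single subjects |
| Expedited reports to IRB and FDA | 3.7 | No, single events |
| Quarterly reports of non-expedited SAEs to the drug supplier | 3.7, reporting of serious adverse events | Not described as by arm |

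**The case against.** A reader might infer from 2.4 that stopping depends on the missing DSMB and so cannot work. The text does not support that. The four parties are joined by an or, and the IRB, the PI and the sponsor can each still act. The sponsor is the investigator's own department (Appendix: Sponsor), which leaves the IRB as the only independent party, but the provision still operates.

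A reader might also infer that nobody could see an imbalance before month 12. That is too strong as well. Statistical Considerations, item 1, says that investigators and study personnel are unblinded, and subjects are seen in one dialysis unit, so the PI can know the arm of each event as it occurs. Serious, related and unexpected events reach the IRB within 7 days, with FDA reports at 7 or 15 days. SAEs that need no expedited report go to the drug supplier quarterly, whether or not they are thought related. This part of the objection stands: the gap is smaller than the annual interval alone suggests. It does not close the gap. Informal awareness is not a planned review. The expedited IRB route is limited to unexpected events, and bleeding is a listed risk, so an excess of expected bleeding in one arm may not trigger it.

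Finally, the timing figures rest on an accrual that the plan only hopes for. That is correct, and the lower figures in step 4 belong with the headline range.

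**Conclusion.** The concern holds on the planned timeline. With uniform entry and the clock starting at first enrolment, 98% (88 subjects) to 100% (70 subjects) of dosing precedes a month-12 review, and about 82% to 83% of the 88 have finished. For 88, about 16 subjects would still be on drug, so it would be wrong to say that no review could take place during exposure. Nor do the documents show that dosing in the trial as run was over by its first review. Under a later start or slower enrolment the share ranges from about 94% down to 37.5%.

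Under every scenario a substantial part of dosing comes before any planned look across subjects, and no comparison by arm is scheduled during dosing. The DSMB mention is an inconsistency of wording. The absence of any rule in 2.4 for 5.3 to apply is a separate contradiction that needs resolving.

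**What to change.** 1. In 5.4, schedule the PI's aggregate review within the dosing period, by arm, and report it to the IRB. Quarterly while any subject is on study drug is one workable interval; no document sets it. On the planned timeline, reviews at months 3, 6 and 9 would fall at about 10% to 13%, 41% to 51% and 79% to 89% of dosing.
2. Specify the data for that review: all documented SAEs, whatever their relatedness, plus the hemoglobin and access bleeding-time data already collected under Biomedical Research, item 1. This is needed because 3.1 restricts AE recording to events both related and serious, while 5.3 lists all adverse events for review.
3. Make 2.4 agree with 5.1, 5.2 and 5.5 on whether a DSMB exists.
4. Reconcile 5.3, which calls for applying stopping rules set out under 2.4, with 2.4, which states none. The content of any such rule is for the investigators and the IRB.

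The cost is a few wording changes, a few extra PI tabulations and short IRB reports. No new committee is needed.

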2.5 What are the criteria for breaking the blind/mask?

NA – Not blinded/masked

2.6 How will subject withdrawals/dropouts be reported to the IRB prior to study completion?

IRB-HSR continuation status form

3. Adverse Event / Unanticipated Problem Recording and Reporting

3.1 Will all adverse events, as defined in section 1.1, be collected/recorded?

No

► IF NO, what criteria will be used?

Only adverse events that are deemed related AND serious

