This study is a randomized, placebo-controlled, single blind clinical trial. Seventy patients with ESRD on chronic HD and a functioning AVF will be recruited. Consent form will be obtained. History and physical, dialysis parameters and laboratory data (CBC, CMP, PTT & INR) will be obtained throughout the study. The following data will be documented on each patient: 1-Age/gender/race/body weight/cause of ESRD 2-Vintage of HD 3-Time since access was placed 4-Type and place of access and blood flow rate of access 5-History of prior access problems 6-Comorbid conditions (Hypertension, coronary artery disease, Diabetes Mellitus, Bleeding problems, peripheral vascular disease). 7-Current medications (Coumadin, Erythropoiesis stimulating agents, heparin, other antiplatelets, digoxin, statins). Patients will be randomized into two groups to receive: Group 1: Ticagrelor 90 mg PO BID Group 2: Placebo drug PO BID.

Subjects will have a screening visit and if they qualify for the study they will have 18 additional visits. All of these visits will occur while the subjects are at their normal dialysis treatment. Subjects will be randomized to either the Ticagrelor group or the placebo group. Subjects will be on study medication for 6 months then they will have a follow up period off drug for 6 months. Subjects will be seen twice a month while on study medication and once a month in the follow up period. While the subjects are on study medication we will assess any side effects of the study medication and put their relation to the study drug at each study visit. We will use clinical monitoring as suggested by Beathard (21). We will document the subject's adherence to the study, if they are hospitalized and what caused their hospitalization. A monthly intra-access flow will be obtained using ultrasound dilution by transonics as part of standard of care. Any change in the clinical assessment of the access, prolonged bleeding (>20 minutes) after removal of needles, trend of decreasing intra-access blood flow as determined by transonic (> 25% or original flow), or an access flow rate < 400 ml/min, will prompt a referral for a fistulogram. If confirmed stenosis (>50% stenosis of the access diameter) an intervention (angioplasty) will be performed. This intervention is part of the subject's standard of care.

Background

1. Provide the scientific background, rationale and relevance of this project.

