1-Age/gender/race/body weight/cause of ESRD

2-Vintage of HD

3-Time since access was placed

4-Type and place of access and blood flow rate of access

5-History of prior access problems

6-Comorbid conditions (Example: Hypertension, coronary artery disease, Diabetes Mellitus, Bleeding problems, peripheral vascular disease).

7-Current medications (Example: Coumadin, Erythropoiesis stimulating agents, heparin, other antiplatelets, digoxin, statins)

This data will be obtained from the dialysis computer system and will be verified with the subject.

8-Physical Exam

9-Vital signs (blood pressure, heart rate, and weight) will be obtained from the subject's dialysis record.

Adverse events and concomitant medications will be reviewed at each study visit. We will also note any access issues at each study visit.

Study Medication Stopping Rules for Prolonged Bleeding:

If post treatment bleeding time is prolonged more than 30 minutes we will stop the study drug and refer for fistulogram,

If bleeding still persists after fistulogram and intervention we will continue to hold the study drug and do work up for bleeding. We will continue to hold study drug for 5 days if signs of increased tendency for bleeding as recurrent Epistaxis > twice in one week, if any evidence of GI bleed, or if Hgb should drop > 1gm in one week. If the bleeding is believed to be drug related or it no resolution occurs the subject will be withdrawn from the study.

We will also hold study drug for 5 days if hemoglobin is consistently less than 8g/dL for 2 consecutive weeks, or hemoglobin dropping 1g/dL in one week.

IRB-HSR# 17224: Randomized, Placebo-controlled, Single Blind, Trial to Determine the Safety and Efficacy of Ticagrelor for Maintaining Patency of Arterio-Venous Fistulae Created for Hemodialysis

For a prolonged bleeding event standard practice will be applied, including: (prolonged bleeding is defined as bleeding more than 30 minutes)

- **Direct pressure.** Any bleeding that warrants an emergency department visit should be immediately controlled with the application of direct digital pressure to the puncture site for 5-10 minutes. Once the bleeding abates, the patient should be observed for rebleeding or early thrombosis for 1-2 hours.

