1.1 How will you define adverse events (AE) for this study?

X An adverse event will be considered any undesirable sign, symptom or medical or psychological condition **even if the event is not considered to be related** to the investigational drug/device/intervention. Medical condition/diseases present before starting the investigational drug/intervention will be considered adverse events only if they worsen after starting study treatment/intervention. An adverse event is also any undesirable and unintended effect of research occurring in human subjects as a result of the collection of identifiable private information under the research. Adverse events also include any problems associated with the use of an investigational device that adversely affects the rights, safety or welfare of subjects.

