1.2 How will you define serious adverse events?

X A serious adverse event will be considered any undesirable sign, symptom, or medical condition which is fatal, is life-threatening, requires or prolongs inpatient hospitalization, results in persistent or significant disability/incapacity, constitutes a congenital anomaly or birth defect, is medically significant and which the investigator regards as serious based on appropriate medical judgment. An important medical event is any AE that may not result in death, be life-threatening, or require hospitalization but may be considered an SAE when, based upon appropriate medical judgment, it may jeopardize the patient and may require medical or surgical intervention to prevent one of the outcomes listed in the definitions of SAEs.

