2.1 What are identified risks and plans to minimize risk

****Please Also Refer to the Investigator Brochure and the Package Insert for Brilinta/ Ticagrelor**

Adverse Events with Brilinta/Ticagrelor

Frequent complaints (seen in at least 3% of study participants) that have been reported during studies:

- Bleeding
- Dyspnea (Shortness of Breath)
- Cough
- Dizziness
- Nausea
- Atrial Fibrillation (Heart Rhythm Disorder)
- Hypertension (High Blood Pressure)
- Non-Cardiac Chest Pain

IRB-HSR# 17224: Randomized, Placebo-controlled, Single Blind, Trial to Determine the Safety and Efficacy of Ticagrelor for Maintaining Patency of Arterio-Venous Fistulae Created for Hemodialysis

- Diarrhea
- Back Pain
- Hypotension (Low Blood Pressure)
- Fatigue
- Chest Pain
- Headache

More Frequent complaints (seen in at least 6 to 7% of study participants) that have been reported during studies:

- Bradycardia (Slow Heart Rate)
- Elevated Serum Creatinine

There have also been cases of increased uric acid levels for subjects taking ticagrelor. A high uric acid level, or hyperuricemia, is an excess of uric acid in your blood. Uric acid is produced during the breakdown of purine, a substance found in many foods. Once produced, uric acid is carried in your blood and passes through your kidneys, where most of it leaves your body when you urinate. A high uric acid level may result in attacks of gout, but not everyone who has high uric acid gets gout, and not everyone with gout has high uric acid. Increased uric acid may also increase the chances of kidney stones. There is also an increased risk of severe bleeding for subjects taking ticagrelor. Due to the increase risk of severe bleeding there may be a risk of delay in any surgery that you may need while taking this study medication.

Expected Risks related to study participation.	Frequency
Reproductive Risks These are unknown at this time.	Minimized due to the requirements of this protocol.
Violation of subject’s privacy and confidentiality	Minimized due to the requirements of the privacy plan in this protocol

2.2 List by bullet format a summary of safety tests/procedures/observations to be performed that will minimize risks to participants:

- Study personnel will be checking on patients twice a month for six months while subjects are on study treatment and once a month while subjects are in the follow up visits.
- We will be monitoring the time it takes for the subject’s access to clot.
- AE monitoring at each visit

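### Section 3.1 records only related, serious adverse events, which cannot supply the primary safety comparison and conflicts with the rule that every SAE be documented

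*Combined protocol and SAP*

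**What the plan says.** Safety, with feasibility, is the primary objective. Statistical Considerations item 4 gives the analysis: "tabulating adverse events and severe adverse events for the two study arms", with a chi-square test of the difference between arms. It sets no condition on cause or seriousness. The same item reports enrolment to date as "23 in the Ticagrelor treatment arm and 20 in the placebo arm".

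Data and Safety Monitoring Plan section 3.1 asks whether all adverse events as defined in section 1.1 will be collected or recorded. The answer is no, and the criterion is "Only adverse events that are deemed related AND serious".

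The text headed Reporting of serious adverse events, after the section 3.7 tables, says that all SAEs will be documented and that all go to the drug supplier whether or not they are thought causally related.

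The surrounding provisions are these:
- Section 1.1 defines an adverse event to include one "even if the event is not considered to be related".
- Section 1.2 counts as serious any event that "requires or prolongs inpatient hospitalization", among other criteria.
- Biomedical Research item 1: "Adverse events and concomitant medications will be reviewed at each study visit". Section 2.2 lists "AE monitoring at each visit".
- The study summary, for the on-drug period: "we will assess any side effects of the study medication and put their relation to the study drug at each study visit".
- Section 3.4 has the principal investigator grade each event as related, possibly related or unrelated.
- Statistical Considerations item 1 says that investigators and study staff know the allocation.

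**The concern.** An event that is never recorded cannot be tabulated. If staff apply section 3.1, the dataset behind the primary safety comparison holds only serious events that the investigator attributes to the study. If they apply the SAE reporting text, it also holds unrelated SAEs. The two rules give different data for the same planned analysis, and the plan does not rank them or define a safety dataset.

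Two things are at stake under section 3.1. The first is power: few events enter, so a real difference is easily missed. The second is bias: whether an event exists in the data at all depends on an opinion about cause, held by someone who knows which arm the patient is in. If attribution differs by arm, so does the recorded rate, even when the true risks are equal.

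Two smaller gaps sit beside this. Item 4 speaks of severe events where sections 1.2 and 3.1 speak of serious ones. Section 3.1 also does not say whether an event graded possibly related counts as related.

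**Working it through.** The plan gives no adverse event rate, attribution share or power for the safety comparison, so there is no stated figure to reproduce. The contradiction rests on the text. The arithmetic only illustrates its consequence.

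**Which events each rule admits**

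| Event | Section 3.1 | SAE reporting text | Item 4 analysis needs it? |
|---|---|---|---|
| Serious, related | recorded | documented | yes |
| Serious, unrelated | not recorded | documented | yes |
| Non-serious, related | not recorded | silent | yes |
| Non-serious, unrelated | not recorded | silent | yes |

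Row 2 is the direct conflict between section 3.1 and the SAE text. Rows 2 to 4 are the conflict with item 4. A hospital admission judged unrelated falls in row 2: it is an SAE under section 1.2 and is excluded by section 3.1.

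**Illustration: inputs.** Arm sizes of 23 and 20 come from item 4. The assumptions are: the unit is a patient with at least one event, the test is two-sided at 5%, and the rates and shares are those shown. Item 4 does not say whether the chi-square is continuity-corrected, so results are given as uncorrected / Yates, with Fisher's exact test as a third check.

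**Method.** Exact enumeration of two binomials, p1 for ticagrelor and p0 for placebo:

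Power = sum over x = 0..23 and y = 0..20 of C(23,x) p1^x (1-p1)^(23-x) × C(20,y) p0^y (1-p0)^(20-y) × [1 if the test gives p < 0.05, else 0].

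*Full recording*

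| True risk, ticagrelor v placebo | Uncorrected / Yates / Fisher |
|---|---|
| 60% v 20% | 79% / 70% / 70% |
| 60% v 30% | 53% / 41% / 43% |
| 50% v 30% | 27% / 19% / 19% |

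*Filtered recording, true risk 60% v 20%.* Recorded rate = true risk × share of affected patients with an event that passes the filter.

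| Share passing, both arms | Recorded rates | Uncorrected / Yates / Fisher |
|---|---|---|
| 50% | 30% v 10% | 35% / 24% / 27% |
| 30% | 18% v 6% | 16% / 8% / 8% |
| 10% | 6% v 2% | 0.7% / 0.1% / 0.1% |

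At a 30% share, the expected number of patients with a recorded event is 23 × 0.18 + 20 × 0.06 = 4.14 + 1.20 = 5.34. The smallest expected cell is then 5.34 × 20/43 = 2.5, where the chi-square approximation is itself doubtful.

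*Unequal attribution.* Suppose the SAE risk is 40% in both arms. If 20% of affected ticagrelor patients and 10% of affected placebo patients pass, the recorded rates are 0.40 × 0.20 = 8% and 0.40 × 0.10 = 4%, a false two-fold ratio. Reversing the shares gives 4% v 8%. These splits reach significance in only 1.6% / 0.4% / 0.5% and 3.0% / 0.8% / 2.9% of trials. The harm there is a distorted estimate and not a false-positive test.

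**The case against.** **Section 3.1 might be only an ethics-board reporting rule.** This does not stand. The question asks what is collected or recorded, reporting has its own section (3.7), and section 3.2 goes on to say how the recorded data are captured.

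**A reader might infer that most of the protocol contradicts section 3.1.** The documents do not support that. Section 1.1 is a definition, and section 3.1 cites it and takes a subset. Reviewing or monitoring events at each visit can precede a filter on what is written down. The study summary speaks of side effects of the drug, which is already attributed wording. All adverse events also appear in the section 5.3 list for aggregate review and in an annual FDA row of section 3.7. But the 5.3 list may have lost its selection marks (it includes dose-escalation rules that do not fit this trial), and the FDA row sits under an investigator-held IND while the Drug Information appendix says IND exempt. Item 4 and the SAE text carry the point.

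**A reader might infer that the primary safety analysis would have no data.** That is too strong. Related serious events would still be recorded. Hospitalization with cause, bleeding time and hemoglobin are collected without a causality filter, although they are not the adverse event tabulation in item 4.

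**The 79% figure flatters full recording.** This stands. It needs a 40-point true difference that nothing in the documents supports. At smaller differences the test is weak even with complete capture, so section 3.1 cannot be blamed for all of the low power.

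**The severe/serious mismatch may be partly an artefact.** This stands in part. Section 3.3 shows several grading scales with no visible selection, and the mark may have been lost in the PDF text. Item 4 still needs to say which is meant.

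**Other fixes exist.** This is fair: narrowing item 4 to all SAEs plus named events would also remove the contradiction. It would give up the comparison of all adverse events that the plan now sets out.

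**Conclusion.** The concern holds as a contradiction between section 3.1 and two other places: the unfiltered primary comparison in item 4 and the rule that every SAE be documented. No passage resolves it. Because safety is part of the primary objective, it must be fixed before the analysis.

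The consequence depends on which rule staff follow. Under section 3.1 the comparison loses all non-serious and all unrelated events, and entry rests on an unblinded causality call, so power can fall and the estimate can be biased in either direction. The documents do not indicate which direction. Under the SAE reporting text an all-cause SAE comparison survives intact, and only non-serious events are lost.

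The size of the effect is illustrative. The fall from 79% / 70% / 70% to 16% / 8% / 8% assumes true risks of 60% v 20% and a 30% share passing in each arm. The textual conflict depends on none of these assumptions.

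**What to change.** Reconcile section 3.1 with Statistical Considerations item 4 and the SAE reporting text:
- Change section 3.1 so that adverse events as defined in section 1.1 are recorded in both arms, with seriousness, severity and the three-level relatedness grade as attributes of each event and not as conditions for entry.
- Run the item 4 comparison regardless of relatedness, and show related and possibly related events descriptively.
- State in item 4 whether severe means a severity grade or serious as defined in section 1.2.

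The cost is protocol wording and more entries on the existing paper forms. Events are already reviewed at each visit, so wider capture is feasible without a new visit procedure. The real downside concerns the 43 patients already enrolled. Their unrecorded events can be recovered only where existing notes contain them, incompletely and by staff who know the allocation. Recovered events should be flagged, and the results shown with and without them.
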